## **EXPERIMENTAL DESIGN**

Overview: Participants are recruited through online recruitment on both social networking sites and alcohol screening sites. If a participant is interested they complete a brief survey online and if they are eligible they are instructed to call the researcher at a time that fits their schedule. The research assistant will review the

eligibility criteria and go over the consent form on the phone. Participants complete a 10 question quiz about the protocol in the form of a consent form quiz to ensure comprehension. They are also trained on filling out the weekly assessment text messages. Once enrolled and randomized, they receive messaging for 12 weeks and complete assessments at baseline, week 4 and week 12 as well as weekly EMA. Once individuals complete the study they will be given a \$40 gift card to amazon. They are compensated \$15 for the baseline survey, \$5 for the week 4 survey, and \$15 for the week 12 survey. Primary outcomes include drinks per drinking day, days heavy drinking, and average drinks per week as measured through week EMA. Additional outcomes will include drinking related consequences, goal commitment and intervention satisfaction.

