### **DISCONTINUATION OF STUDY/SUBJECT WITHDRAWAL**

If a participant self-reports worsening of their condition as a result of the study procedures they will be withdrawn. All participants data will be reviewed at week 4. For those who report their condition has gotten worse, we will call them and inquire about their current symptoms and discontinue them from the study if necessary. Participants can withdraw at any time and we provide referrals. We provide referrals to internet screening sites and treatment using the SAMHSA Treatment finder. We inquire about reasons for withdrawing.

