### **ADVERSE EVENTS**

The Principal Investigator and Co-Investigators are clinical psychologists and licensed Ph.D. social workers and will be responsible for distinguishing between a Serious Adverse Event (SAE) and a non-serious adverse event (AE). All SAE and AE will be reported to the IRB of the NSLIJ according to NSLIJ HRPP policies and to the National Institute of Alcohol Abuse and Alcoholism (NIAAA) project officer within 48 hours of its occurrence. Additionally, the PI will prepare an annual report summarizing all SAE and AE to be submitted to the NIAAA project officer and the IRB. In addition to preparing for SAE, participants' alcohol use will be monitored. Participants will be referred for appropriate treatment according to their needs and wishes if they show severe deterioration, and continued evaluation of participants through assessments will provide ongoing information concerning their clinical status. Significant deterioration is

defined as a significant increase in drinking since the baseline interview; or other indicators through any interaction with the research staff. If any of these indicators are present, the participants will be immediately withdrawn from the study and referred to immediate and appropriate treatment. Primary responsibility and decision making in regards to participants remaining in or being withdrawn from the study will lie with the principal investigator.

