#### Data Management & Analysis

Analyses will be conducted separately on two overlapping samples. All randomized subjects who received at least two days of text messages will be included in the first set of analyses as long as they have some follow-up data on primary analyses. This represents our main outcome analysis. We also will conduct a “worst-case” analysis in which subjects lost to attrition will use their pre-treatment drinking as their week 12 drinking data. Finally, in step three, we will conduct “completer analyses” on those patients completing a full course of messaging. This latter approach to analysis, although subject to more bias, attempts to provide an estimate of the maximal effect of the treatments under ideal conditions. Similar results with all three approaches would increase confidence in the findings. Effect size estimates along with significance levels will be generated for all comparisons. A goal of the study is to determine a reasonable effect size estimate and to assist in planning larger studies of the intervention if findings justify that next step. The critical effect size estimate is of drinking outcomes. The sample sizes of 30-40 per group will provide reasonable estimates of the differences in means.

There are two primary outcome variables: 1) Average drinks per week (sum of drinks drinking day) over the course of the study and 2) the percent of total days in which there is heavy drinking over the course of the study; This data will be collected via the Baseline, Week 4 and Week 12 assessments. Various summary statistics will also be computed, and significantly skewed distributions will be appropriately transformed prior to statistical analysis (e.g. Shapiro–Wilk test). As exploratory secondary analyses we will compare study arms on differences in key secondary outcome variables assessed at baseline and week 12 including alcohol related consequences and drinking norms.

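### If participants withdrawn because their drinking rose count as lost to attrition, the worst-case rule gives them a week 12 value below their last report, so for them it is not a pessimistic bound

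*Protocol*

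**What the plan says.** Data Management & Analysis plans three analyses. The main one takes randomized participants with at least two days of messages and some follow-up data. The second, labelled worst-case, fills gaps by this rule: "subjects lost to attrition will use their pre-treatment drinking as their week 12 drinking data". The third is restricted to those who complete the full course of messaging. The section then draws an inference: "Similar results with all three approaches would increase confidence in the findings".

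Adverse Events treats significant deterioration as "defined as a significant increase in drinking since the baseline interview", or other indicators noticed by staff. If any is present, "the participants will be immediately withdrawn from the study and referred to immediate and appropriate treatment". It adds: "Primary responsibility and decision making in regards to participants remaining in or being withdrawn from the study will lie with the principal investigator". Discontinuation of Study/Subject Withdrawal says that people who report at week 4 that they are worse will be telephoned, and that staff will "discontinue them from the study if necessary".

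The drinking outcome is "Average drinks per week (sum of drinks drinking day) over the course of the study", collected at baseline, week 4 and week 12. The Experimental Design overview instead describes "average drinks per week as measured through week EMA". The protocol does not define lost to attrition, and gives no separate rule for the week 12 data of withdrawn participants.

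**The concern.** Carrying baseline forward assumes that a dropout gained nothing. That is a usual conservative choice for someone who simply stops responding. It is not conservative for someone removed because drinking went up: the imputed value then assumes a return to baseline after reported worsening.

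The withdrawal rule also makes the missing data depend on the outcome, because the people it removes are selected for high drinking. The completer analysis leaves them out as well, since their messaging was stopped. On this reading, two of the three analyses carry none of the reported deterioration to week 12, yet agreement among the three is to be read as support. What is at stake is how much that agreement is worth.

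**Working it through.** **The plan's own figure.** The protocol expects 30-40 per group after 20% attrition. From 240 participants: 240/5 x 0.80 = 38.4; counting the goal-only group as a sixth, 240/6 x 0.80 = 32; setting aside the 15 already placed in that group, (240 - 15)/5 x 0.80 = 36. All fall within the stated range. The protocol gives no SD or target effect, and no expected number of deterioration withdrawals.

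**The logical step.** Let B be baseline drinking and L the last report. Withdrawal on the drinking criterion means L > B by the protocol's own definition. The rule sets week 12 = B, so the imputed value is below L by L - B > 0. No outside figure is needed.

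**Size per person (rises assumed).**
- B from 12 drinks/week (entry floor for women) to 24 (severity cut for men in the Randomization section, read as per week).
- Assumed rise of 25% to 50%.
- Gap: 12 x 0.25 = 3 to 24 x 0.50 = 12 drinks/week.

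**Effect on an arm mean at week 12.** Arm size 240/5 = 48.
- One such person: 3/48 = 0.06 to 12/48 = 0.25.
- An assumed quarter of 20% attrition, 0.25 x 0.20 x 48 = 2.4 people: 2.4 x 3/48 = 0.15 to 2.4 x 12/48 = 0.60.

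**Effect on the outcome over the study.** The rule replaces week 12 only. If weeks 4 and 12 are averaged equally and week 4 was observed, these halve to 0.03-0.13 and 0.08-0.30. They shrink further if weekly text-message data are used.

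**Scale for comparison.** SE of a two-arm contrast = SD x sqrt(2/48): 1.63 for an assumed SD of 8 and 3.06 for 15. The week 12 shift is therefore between 0.06/3.06 = 0.02 and 0.60/1.63 = 0.37 SE. For one person it is at most 0.25/1.63 = 0.15 SE, and for the averaged outcome at most 0.30/1.63 = 0.18 SE.

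**Bias of the obvious substitute.** Suppose the larger of B and L is imputed and the rise is pure noise, with independent reports of equal mean and within-person SD s. Without selection, the maximum is biased upward by s/sqrt(pi): 2.26 for s = 4 and 4.51 for s = 8. These people, however, are selected for a rise above some threshold t, so the bias is (s/sqrt(2)) x phi(z)/(1 - Phi(z)) with z = t/(s x sqrt(2)):

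| s (assumed) | t (assumed) | z | Bias, drinks/week |
|---|---|---|---|
| 4 | 6 | 1.061 | 4.5 |
| 4 | 12 | 2.121 | 7.0 |
| 8 | 6 | 0.530 | 6.6 |
| 8 | 12 | 1.061 | 8.9 |

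This is of the same order as the 3-12 drink gap being corrected. Spread over an arm of 48, one person contributes 4.5/48 = 0.09 to 8.9/48 = 0.19.

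**The case against.** The case against has several sound parts.

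- **The condition is not stated.** The withdrawal sections speak of withdrawing and discontinuing, not of attrition, and a SAP may settle who falls under the rule. Adverse Events also mentions ongoing evaluation through assessments. If week 12 were still collected, nothing would be imputed. This stands as a limit, although immediate withdrawal from the study points the other way.
- **Missing data are also examined elsewhere.** The statistical section plans a random-effects look at patterns of missed data. That adds information on dropout but does not change the worst-case rule or what its label implies.
- **The subgroup may be nearly empty.** The principal investigator decides on withdrawals, other indicators can trigger them without a rise in drinking, and the protocol reports no adverse events among the first 104 enrolled (104/240 = 43%). This does not show that nobody was withdrawn, but it suggests few.
- **A high last report is not week 12 drinking.** A seven-day text report and a 90-day baseline questionnaire differ in recall window, and regression to the mean is substantial.
- **The label is explained where it is used.** A careful reader can see what is computed. The inference from agreement is nevertheless stated without qualification.

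A reader might infer that the rule understates true week 12 drinking, that it favours one arm, or that the main result is biased. The documents support none of these. Drinking after referral is unknown, the split of such withdrawals between arms is unknown, and the rule applies only to the worst-case analysis.

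**Conclusion.** The point holds as a minor one, on the condition that deterioration withdrawals count as lost to attrition. For them the worst-case value lies below the last report, so it is not a pessimistic bound, and agreement of the three analyses is somewhat weaker reassurance than the protocol says. The claim is only about the last report, not about true drinking at week 12.

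The numerical effect is at most about 0.4 SE in one sensitivity analysis of an exploratory study, and probably much less. That figure rests on assumed rises, an assumed number of such withdrawals and assumed SDs. The more useful observation is that the withdrawal provision itself can create outcome-dependent missing data, which the trial could largely avoid.

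**What to change.** 1. **Separate stopping messages from leaving the study.** Reword the withdrawal provision in Adverse Events so that participants stopped for deterioration leave the messaging but are still invited to complete the existing weekly text items and the week 4 and week 12 web surveys, unless they withdraw consent. Referral and clinical decisions stay as they are. Use these data in the analysis. Cost: an IRB amendment in an enrolling trial, and some non-response. Follow-up is already remote and no new instrument is needed.

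2. **Rename the rule and add one run.** Call the present rule baseline carried forward. Where week 12 is still missing for someone withdrawn for increased drinking, add a deliberately pessimistic sensitivity run using the larger of baseline and last report. State that this value is in effect a last observation selected for being high, that it mixes 90-day, 30-day and seven-day recall, and that it is biased upward by roughly 4.5-9 drinks/week per person under the SDs and thresholds assumed above. Do not extend it to other dropouts: even the unselected bias of 2.26-4.51, applied to 20% of an arm, would add 0.45-0.90 to its mean, more than the problem itself. Cost: a little programming.

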**Follow-up Assessment:** We will conduct a brief web-based week 4 assessment to assess drinking variables and overall functioning. This is 15-20 questions. Three days before their 12-week completion date participants will be sent a reminder text and email to complete the final assessment via a web-based survey. The week 12 assessment will include all the baseline measures as well as an item on perceived relevance of the intervention content to them specifically (Strecher, Shiffman, & West, 2006), treatment history during the intervention, overall recommendations to improve the intervention in addition to additional resources for PD. During the course of the study, additional data elements such as the number of eligible vs. ineligible participants, reasons for exclusion, referral sites, length of time to complete the screening and each assessment, and numbers of persons who drop out at any point in the study and at which point they drop out.

**Ecological Assessment:** Once the study begins all subjects will receive weekly ecological assessment for assessment only purposes (TA arm will also receive interactive assessment). **Weekly Drinking:** Three items will be sent every seven days including: The number of drinking days in the last week, the average number of drinks per drinking day in the last week, and number of drinking days where more than 5 drinks were consumed (4 for women) in the last week. We will also ask about

improvement over the course of the week to both assess change but also guide the adaptive intervention group. We chose this time to send messages during the day to reduce the chances that individuals will be intoxicated while reporting their drinking in their natural environment. Shiffman (2009) highlights the use of EMA to collect data from drinking and substance abusing populations and highlights while some have shown mild intervention effects (e.g. Collins et al., 1998) that most show little reactivity. Moreover, collecting weekly drinking assessments should reduce the likelihood of reactivity.

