**Measures & Schedule of Events (See Attached)**

Measure	Construct	Time					Optional Messaging
		Screen	Intervention Messaging Period			Weeks 12-24	
			Baseline (Randomize)	Weekly EMA	Week 4	Week 12	
Demographics	-	X	X			X	
QFV-30 questionnaire*	Alcohol consumptions last 30 days	X			X		
QFV-90 questionnaire*	Alcohol consumptions last 90 days		X			X	
EMA (Drinking Days, Drinks per Drinking Day, Heavy Drinking Days)	Weekly alcohol consumption			X			X
Frequency of Drug Use	Frequency drug use last 30 days	X				X	
Tx History & Medications	Substance abuse and mental health treatment history (last year) and current medications.	X				X	
Short Alcohol Withdrawal Scale*	Alcohol withdrawal potential	X					
Short Inventory of Problems*	Alcohol related consequences		X			X	
3-Item Primary Appraisal Measure: Alcohol	Subjective harm from use, continued use and benefit to stopping		X		X	X	
The Obsessive-Compulsive Drinking Scale*	Craving, salience and loss of control over alcohol		X			X	
Drinking Norms Rating Form	Perceptions of participants own and others drinking behavior		X			X	
Drinking Goals	Daily and weekly consumption goals	X	X		X	X	
Typical Drinking Patterns	When individuals are most likely to drink heavily		X		X	X	
Goal Commitment	Commitment to moderation and individual goals		X	X	X	X	
Single item rulers	Readiness to change, importance, and confidence to change.		X		X	X	
Triggers Questionnaire	Situations that may trigger heavy drinking		X			X	
Relevance of intervention to needs	Single item on whether material was relevant to participant				X	X	

Other sources of help sought	Outside help sought during the intervention					X	
Satisfaction and recommendations	Overall program satisfaction and recommendations.					X	

\*Validated scales

A brief description of the site(s) where the research is to be conducted, including information about the adequacy of facilities for the safe and appropriate conduct of the research, and relevant demographic and epidemiological information about the country of region concerned.

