### **CRITERIA FOR EVALUATING RESPONSE/STATISTICAL ANALYSIS**

The aims of this proposal are consistent with the initial sub-stages of Stage I developmental research described in the Stage Model of Behavioral Research (Rounsaville, Carroll & Onken, 2001). Primary Aim 1: To develop an adaptive text messaging program for problem drinking. 1A. Develop a brief assessment, normative feedback and list of text messages based on the PD intervention literature & obtain outside review from thought leaders. 1B. Survey 40 problem drinkers on overall SMS intervention preferences including message content and timing and frequency

preferences. 1C. Develop SMS intervention, review with thought leaders and pre-pilot and test with 10 problem drinkers and modify intervention based on feedback. Primary Aim 2: : To test whether the Tailored-adaptive treatment arm is superior to the content tailored only arm and the consequence messaging arm in reducing weekly drinking/drinks per drinking day and percent days heavy drinking over the course of the 12 week intervention. Hypothesis 2a: Tailored-adaptive (TA) arm will be superior to the content tailored only and consequence messaging study arms in weekly drinking/drinks per drinking day. Hypothesis 2b: Tailored-only messaging will be superior to consequence messaging in reducing weekly drinking/drinks per drinking day. Hypothesis 2c: All supportive messaging arms will be superior to assessment only in reducing weekly drinks weekly drinking/drinks per drinking day. Hypothesis 2a: TA will be superior to TO & CM in reducing weekly drinking/drinks per drinking day. Hypothesis 2b: TO will be superior to CM in reducing weekly drinks. Hypothesis 2c: All supportive messaging arms will be superior to EMA only in reducing weekly drinking/drinks per drinking day. Other outcomes include percent heavy drinking days and drinking days.

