Data will be cleaned, summary variables created, missing data evaluated, and distributions assessed for normality. Equivalence of the random assignment of groups on key baseline characteristics will be assessed, and in the unlikely event that groups differ significantly on any characteristics, we will run analyses both with and without these variables as covariates to determine whether baseline differences may account for differences in outcomes. Gender and race/ethnicity differences will be evaluated and these variables included as covariates if they are correlated with outcomes. We will aggregate daily EMA into use weekly summary data, as it allows us to examine the trajectory of drinking patterns week by week over the course of the 12-week study.

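### The protocol gives conflicting sets and data sources for its primary drinking outcomes and does not say which prevails

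*Protocol*

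**What the plan says.** - Protocol, Experimental Design (Overview): "Primary outcomes include drinks per drinking day, days heavy drinking, and average drinks per week as measured through week EMA". That is three outcomes from weekly text-message assessment.
- Protocol, Data Management & Analysis: "There are two primary outcome variables: 1) Average drinks per week (sum of drinks drinking day) over the course of the study". The second is the percentage of days with heavy drinking. Drinks per drinking day is not listed. On the source: "This data will be collected via the Baseline, Week 4 and Week 12 assessments".
- Protocol, Criteria for Evaluating Response/Statistical Analysis: Primary Aim 2 tests superiority "in reducing weekly drinking/drinks per drinking day and percent days heavy drinking over the course of the 12 week intervention". The same section then adds: "Other outcomes include percent heavy drinking days and drinking days". It also states Hypothesis 2b twice, once for weekly drinking/drinks per drinking day and once for weekly drinks only.
- The same section, on data handling: "We will aggregate daily EMA into use weekly summary data". The Ecological Assessment paragraph, however, describes the drinking items as weekly: "Three items will be sent every seven days". The description of the EMA-only arm agrees with that.
- The Measures & Schedule of Events table puts the 90-day QFV ("Alcohol consumptions last 90 days") at baseline and week 12, and the 30-day QFV at screening and week 4. The weekly items have no baseline mark.

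**The concern.** The two main statements differ in the number of primary outcomes, in the status of drinks per drinking day, and in the instrument. The result presented as primary could therefore be settled after the data are seen. That matters even in an exploratory trial, because its declared product is an effect size on drinking for planning a larger study, and that number depends on the choice.

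The source also decides who is analysed. Data Management & Analysis admits a participant to the main analysis only if some follow-up data exist on the primary measures. Someone who answers the Sunday texts but skips both follow-up surveys is in under one statement and out under the other.

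**Working it through.** **Statements side by side**

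| Place in protocol | Primary outcomes | Source |
|---|---|---|
| Experimental Design, Overview | drinks per drinking day; heavy drinking days; drinks per week | weekly text items |
| Data Management & Analysis | drinks per week; percent heavy drinking days | baseline, week 4 and week 12 surveys |
| Primary Aim 2, statistical section | weekly drinking/drinks per drinking day; percent heavy drinking days (later listed among other outcomes) | not stated |

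The first two rows share drinks per week and heavy drinking days; count against percentage is only a rescaling. They disagree on the number of outcomes, on drinks per drinking day, and on the source.

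**Recall windows.** Inputs: 30 and 90 days from the measures schedule, and a 12-week (84-day) intervention. Assumptions: day 0 is baseline, and the surveys are completed at exactly days 28 and 84. Data Management & Analysis does not name the QFV; I infer it from the schedule as the consumption measure at those visits.

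- Week 4 QFV-30: 28 − 30 = −2, so days −2 to 28.
- Week 12 QFV-90: 84 − 90 = −6, so days −6 to 84.
- Overlap: all 30 days of the first window, which is 30/90 = one third of the second.
- The twelve weekly reports cover days 0 to 84 in separate weeks.

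The two surveys are therefore not successive periods, and both reach slightly before baseline.

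**Share of weight by period**

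| Summary | Weeks 1–4 | Weeks 5–12 | Before baseline |
|---|---|---|---|
| Mean of 12 weekly reports | 4/12 = 33% | 8/12 = 67% | 0 |
| Week 12 QFV-90 alone | 28/90 = 31% | 56/90 = 62% | 6/90 = 7% |
| Week 4 QFV-30 alone | 28/30 = 93% | 0 | 2/30 = 7% |
| Equal average of the two surveys | ½(28/30 + 28/90) = 62% | ½(0 + 56/90) = 31% | ½(2/30 + 6/90) = 7% |

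**Consequence for an effect.** Assume accurate recall and an effect of size D that is zero in weeks 1–4 and constant from week 5. Each summary then estimates D times its share for weeks 5–12:

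- weekly reports: 0.67D
- week 12 QFV-90 alone: 0.62D, a ratio of 0.62/0.67 ≈ 0.93 to the weekly reports
- equal average of the two surveys: 0.31D, a ratio of 0.31/0.67 ≈ 0.47
- week 4 QFV-30 alone: 0

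**Worst-case analysis.** Data Management & Analysis replaces the week 12 value of a participant lost to attrition with pre-treatment drinking. That is a single time point, while the primary outcome is an average over the study. With the weekly items as source, the replacement would also come from another instrument, because those items have no baseline.

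**The case against.** The trial is declared exploratory, the protocol sets no alpha, and effect sizes are promised for every comparison, which limits selective reporting. Overlapping recall is a defect only if the two surveys are analysed as separate periods, and no stated model does that. The most natural survey summary, the week 12 QFV-90 alone, is close to the weekly mean. All of this stands and limits the size of the problem, but none of it says which outcomes and source are primary. A separate analysis plan might choose, but the protocol would still contradict itself.

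A reader might infer three stronger points that the protocol does not support.

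- *Three incompatible definitions.* The statistical section is not a clean third version. Its Primary Aim 2 keeps percent heavy drinking days and only later lists it among other outcomes. That is an internal inconsistency.
- *The survey version mis-weights the 12 weeks and loses more than half of a late effect.* This needs an equal average of the week 4 and week 12 surveys, which the protocol nowhere proposes.
- *The reference to daily EMA means that the tailored-adaptive arm is measured differently from its comparators.* That arm does receive extra interactive assessment, but the Ecological Assessment paragraph gives all arms the same weekly items and names the interactive part separately. Nothing routes the interactive replies into the outcome. The word daily is a wording error to correct; no bias is shown.

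**Conclusion.** The contradiction is real and stands in the current text: three primary outcomes from weekly items against two from web surveys, plus an inconsistent status for percent heavy drinking days. Its numerical effect depends on how the surveys would be used. For an effect that appears only from week 5, it ranges from slight (0.62D against 0.67D) to more than half (0.31D against 0.67D). The larger figure holds only for a summary that the protocol does not state. These figures rest on surveys at days 28 and 84, accurate recall, and the inference that the QFV supplies the survey data. The difference in who qualifies for the main analysis needs none of these assumptions.

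**What to change.** By dated amendment, made before any between-arm outcome data are examined, state one primary outcome set, one source and one time window. Use the same wording in the Objectives, the Experimental Design overview, the statistical section and Data Management & Analysis. The date matters because the safety text shows that at least 104 people were already enrolled.

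The weekly items are the natural source for an average over the study, because every arm receives them and two sections already point to them. A consistent version would be:

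- average drinks per week over weeks 1–12 (drinking days × average drinks per drinking day) and percent heavy drinking days, both from the weekly items;
- an explicit status for drinks per drinking day, which the aims and the overview treat as primary and Data Management & Analysis omits;
- the baseline QFV-90 as covariate and the week 12 QFV-90 as a sensitivity outcome;
- the reference to daily EMA replaced by the common weekly items, with a clarifying statement that the tailored-adaptive arm's interactive replies do not enter the outcome;
- the worst-case rule rewritten to fit the chosen outcome.

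The cost is an amendment; every item is already collected in all arms. The downside is missed weekly replies. The week 12 QFV-90 helps only in part, since people who stop replying may also skip that survey.
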